### ***Procedures to maximize compliance with study visits***

Several methods will be used to maximize the proportion of participants who routinely keep their study visit appointments. First, only individuals with an expressed interest in participating and keeping appointments will be enrolled. Second, at enrollment, information will be collected including the participant's name, address, phone number, and, with the permission of the participant, names and telephone numbers of friends/relatives who would normally know the participant's whereabouts. Each participant will be contacted on the day prior to the scheduled clinic visit. If the participant cannot be reached at the primary phone number listed, every effort will be made to contact him/her at the secondary numbers listed for friends/relative. Third, participants will be given written appointment cards. Fourth, participants with telephones may be called the day before the scheduled visit to remind them. Fifth, participants who miss appointments will be contacted either by phone or by domiciliary visit or through friends/family whose names were provided by the participant. Finally, study participants will be compensated for their time and travel to and from study visit. The form and amount of compensation will be in accordance with local guidelines.

### ***Informed Consent***

Participants enrolled in the study will be approached and invited to participate in the study when they present for TB evaluation and care at the CHBH, or local clinics in Soweto. Individual informed consent will be obtained by trained study personnel using Ethics Committee/IRB-approved consent forms. The study will be explained to potential participants using an information sheet available in the common local languages (e.g., Sesotho, isiZulu). If a participant is unable to read or write, witnessed verbal consent will be obtained. Informed consent is a process that will be initiated prior to the individual's agreeing to participate in the study and will continue throughout the individual's study participation. Discussion of risks and possible benefits of study participation will be provided by designated study staff to potential participants. Potential participants will receive counseling about study objectives and procedures, potential risks and benefits, and the informed consent process. The participants will have the opportunity to discuss the study with their surrogates or think about it prior to agreeing to participate. A copy of the signed and

dated informed consent document will be offered to the participants for their records. The rights and welfare of the participants will be protected by emphasizing to participants that the quality of their medical care will not be adversely affected if they decline to participate in this study, and that they may withdraw consent at any time. The investigator will retain a copy of the signed consent forms, which may be inspected at the monitor's/auditor's request. The investigator will promptly report to the Ethics Committee/IRB of all changes in the research activity and all unanticipated problems involving risks to human subjects or others, and will not make changes in the research without Ethics Committee/IRB approval, except where necessary to eliminate apparent immediate hazards to human subjects.

In South Africa, patients are provided free access to TB care, and HIV testing and treatment through the public sector. According to current South African National Department of Health guidelines, HIV-seropositive patients with a CD4+ count <500 cells/ $\mu$ L should be advised and encouraged to start ART without delay. The current first line ART regimen in South Africa is a fixed-dose combination containing tenofovir, emtricitabine, and efavirenz.

Diagnosis and treatment of TB is provided for free through public sector TB Clinics and hospitals in South Africa. GeneXpert testing, which can rapidly and accurately detect *Mycobacterium tuberculosis* and rifampin resistance, is available at public health facilities in South Africa, including at PHRU and SomCHAT. GeneXpert will be used at study sites to diagnose pulmonary TB and exclude patients with rifampin resistance, which is a surrogate for multi-drug resistance (MDR). Phenotypic drug susceptibility testing will be routinely performed on all isolates from participants enrolled in the study to confirm susceptibility to all first-line drugs.

### ***Contraception***

Females may participate if they are: 1) of non-childbearing potential (have had a bilateral oophorectomy, tubal ligation and/or hysterectomy or have been postmenopausal for at least 12 consecutive months), 2) if they are using effective barrier birth control methods and are willing to continue practicing birth control methods throughout treatment or 3) have a vasectomized male partner (confirmed sterile), or have a female partner. Therefore, to be eligible for this study women of childbearing potential should either: 1) use a double barrier method to prevent pregnancy (i.e. use a condom with either diaphragm or cervical cap) or 2) use an intrauterine device in combination with a barrier contraceptive. They must also be willing to continue these contraceptive measures until one week after the last dose of study medication or one week after discontinuation from study medication in case of premature discontinuation. (Note: Hormone-based contraception alone may not be reliable when taking rifampin-containing TB regimens; therefore, hormone-based contraceptives alone cannot be used by female participants to prevent pregnancy).

### ***Safety and Tolerability Endpoints***

The primary endpoint for analysis of safety and tolerability is Grade 3 or higher adverse events. Secondary endpoints include permanent discontinuation of assigned study regimen for any reason (other than new recognition of participant ineligibility based on absence of *M. tuberculosis* growth in baseline sputum cultures, or growth of *M. tuberculosis* resistant to rifampin by GeneXpert. Other aspects of safety and tolerability that will be assessed include mortality and the rates and types of toxicity thought related to study drugs by the Investigator.

### ***Safety Evaluation***

Participants will be carefully monitored to assure safety and detect and manage adverse events. Since treatment will be directly observed, a trained member of the team will assess participants daily for adverse

events. Specific tests to identify statin activity and potential toxicity will be performed at baseline (screening or Day 1) and Days 7, 15, and 30, and will include a serum chemistry panel and CK. A Data and Safety Monitoring Board (DSMB) will review the study protocol and oversee progress of the trial. The DSMB will review safety data after the recruitment of each dosing cohort. Since this is an open-label study, the DSMB will have access to treatment group assignment. The DSMB will be comprised of at least the following: an expert in statistics, clinical trials, clinical TB and statins. No early stopping rules will be formally adopted.

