### ***Data Capture Methods***

Data capture will be accomplished via a set of study-specific paper source documents which have been developed for use in direct recording of data and observations during the patient visits. These records will be included in the patient chart as source records. Data captured during the patient visits will be reviewed to assure accuracy and completeness according to site quality procedures. Once reviewed, these data will be entered into the study database by manual data entry. The study database will be maintained on JHU servers. Data in the study database will be reviewed by site personnel and monitored according to site procedures. All data management for this study will be performed manually, without the aid of a computerized data management system, for which computer system validation would be required.

Reports. The timing of reports will be detailed in the Data Management Operations Manual. Briefly, safety data will be reviewed by the DSMB after 50% of the participants have been enrolled and annually thereafter; reports for the DSMB will be prepared for the DSMB according to a schedule determined at the first convened DSMB meeting.

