## ***Data Analysis***

The current study is a 2-week, 4-arm dose-escalation trial to determine the safety/tolerability and PK of pravastatin when co-administered with the standard drug regimen for drug-susceptible TB (Rifafour). Participants will receive standard anti-TB therapy and pravastatin beginning at a dose of 40 mg once daily. Each subsequent arm (pravastatin 80 mg, 120 mg, and 160 mg) of this study will continue to recruit participants until at least 10 participants in each group are evaluable for full PK analysis.

The primary endpoints in this study are safety/tolerability and pravastatin exposures. A regimen will be deemed safe and well tolerated if none of the participants require treatment discontinuation for a pravastatin-related adverse reaction and  $\leq 3$  participants experience a pravastatin-related grade 3 (or higher) adverse event during the 14-day study period and follow up. PK parameters (e.g., area under the concentration-time curve over 24 hours ( $AUC_{0-24}$ ), minimum concentration ( $C_{min}$ ), maximum concentration ( $C_{max}$ ), and oral clearance (Cl/F)), will be estimated for pravastatin from intensive sampling data after a single dose of pravastatin (baseline PK, prior to initiation of TB treatment) and after 14 days of co-administration with the first-line anti-TB regimen. Based on PK data of pravastatin when co-administered with rifampin ( $T_{max} = 1$  hour,  $T_{1/2} = 1.5$  hours), plasma samples will be collected for pravastatin measurements by LC-MS/MS at the following time points: pre-dose, 0.5 hrs, 1 hr, 1.5 hrs, 2 hrs, 3 hrs, 4 hrs, 6 hrs, and 8 hrs. Pravastatin exposures will be calculated using a noncompartmental approach using standard PK software, e.g., Phoenix WinNonLin. Using all PK data, a PK/PD model will be developed to evaluate the relationship between drug exposures (e.g.,  $C_{max}$ ,  $T_{max}$  or  $AUC_{0-24}$ ) and outcomes (e.g., safety/tolerability).  $C_{max}$  and  $t_{max}$  will be taken directly from the original data. The terminal log-linear phase of the plasma concentration-time curve will be identified visually for each curve.

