### ***Decision-making algorithm for pravastatin safety/PK study:***

Scenario/Pravastatin Dose	Safe/tolerable?	<math>AUC_{0-24}</math> reduction	Decision
1 40 mg daily	Y	=	Increase dose to prava 80 mg and enroll additional participants
2 40 mg daily	N	=	Enroll 5 additional participants (10 total) and discontinue study

3 80 mg daily	N	=	Discontinue study
4 80 mg daily	Y	< 40%	Discontinue study
5 80 mg daily	Y	≥ 40%	Increase dose to prava 120 mg and enroll additional participants
6 120 mg daily	N	=	Discontinue study
7 120 mg daily	Y	<40%	Discontinue study
8 120 mg daily	Y	≥ 40%	Increase dose to prava 160 mg and enroll additional participants
9 160 mg daily	N	=	Discontinue study
10 160 mg daily	Y	=	Study complete

Safety/tolerability: Y= Yes; <3 participants with  $\geq$  one grade 3 (or higher) event of musculoskeletal symptoms, creatine kinase elevation, or liver function test elevation attributed to study drug (probable or definite)

N= No; For Arm 1 (pravastatin 40 mg daily):  $\geq$  1 participant with  $\geq$  one grade 3 (or higher) event of musculoskeletal symptoms, creatine kinase elevation, or liver function test elevation attributed to study statin medication (probable or definite).

For Arms 2, 3, and 4:  $\geq$  3 participants with  $\geq$  one grade 3 (or higher) event of musculoskeletal symptoms, creatine kinase elevation, or liver function test elevation attributed to study statin medication (probable or definite)

$AUC_{0-24}$ = Area-under-the-plasma-concentration-time curve for 24-hour exposure

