#### ***Decision-making algorithm for initiating new dosing cohorts***

The study will be monitored by a DSMB, which will review the safety data for each cohort and will give approval before initiation of each possible dose escalation. Specifically, study drug dose will not be escalated and the study if any three participants develop grade 3 or higher musculoskeletal/CK-related adverse events (AEs), LFT-related AEs ( $> 5 \times UNL$  without symptoms, but  $> 3 \times UNL$  with symptoms or bilirubin  $> 2 \times ULN$ ) or any type of grade 4 event regardless of causal attribution. Study drug dosage will be escalated only if the dose is deemed safe/tolerable based on the above rules and the mean pravastatin AUC is reduced by  $\geq 40\%$  relative to the pre-Rifafour value. Study participants in whom the study drug has been discontinued will remain in the study until the final clinical visit and laboratory evaluation. In the event of study product discontinuation, management of the standard-of-care TB drugs will revert to the site clinician as per national guidelines.

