#### ***Early stopping rules***

Early stopping of the study will be considered if adverse events occur in a great proportion or with greater severity than would be expected at the dosage of the study drug being used based on the safety profile in patients with cardiovascular disease. Upon reviewing the AE data, the DSMB will make a formal determination about early stopping of the study.

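### No legible rule pauses new starts at the current dose, or brings in the DSMB, after a death or life-threatening event within a cohort; a few lines of protocol wording would fix this

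*Combined protocol and SAP*

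**What the plan says.** **DSMB timing and powers.** Safety Evaluation (section 4) has the DSMB review safety data once each dosing cohort has been recruited, and closes with "No early stopping rules will be formally adopted". In section 18, under the algorithm for new dosing cohorts, the DSMB "will review the safety data for each cohort and will give approval before initiation of each possible dose escalation". Under Early stopping rules, also in section 18, stopping is considered if adverse events are more frequent or more severe than expected: "Upon reviewing the AE data, the DSMB will make a formal determination about early stopping of the study". Data Capture Methods (section 10) gives a different calendar: "safety data will be reviewed by the DSMB after 50% of the participants have been enrolled and annually thereafter". The same paragraph lets the DSMB fix its report schedule at its first meeting.

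**Count rules.** The safety/PK decision table in section 18 counts participants with grade 3 or higher musculoskeletal, CK or liver events attributed to the statin. If 40 mg fails that test, the action is "Enroll 5 additional participants (10 total) and discontinue study". Data Analysis adds a separate definition of a safe regimen, under which "none of the participants require treatment discontinuation for a pravastatin-related adverse reaction". The algorithm for new cohorts bars escalation when three participants have listed events, "or any type of grade 4 event regardless of causal attribution". A second consequence, for the study, is begun in that sentence but has no verb.

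**SAE distribution.** Section 5 sends SAEs to DAIDS within 3 days, and information to the FDA, the sponsor, the review boards, the investigators and the South African regulator. The DSMB is not listed.

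**The concern.** An approval gate between cohorts acts only when a cohort is complete. Suppose the third of ten participants at 160 mg dies or has a life-threatening event. The affected participant stops drug and the SAE is filed. Nothing readable then obliges anyone to tell the body that approved the dose, or to hold the fourth participant's start until that body has looked.

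This matters most in Arms 3 and 4. Those doses exceed the highest recommended dose of 80 mg, and section 15 justifies them by rifampin's expected reduction of exposure. Under the pharmacokinetic schedule, however, the Day 1 dose is given alone, and the Day 2 dose is followed by a 4-6 hour sample before the first TB dose. Each entrant therefore takes two doses before the study's first rifampin dose.

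**Working it through.** **1. Does any section pause new starts at the current dose after one such event?**

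- Safety Evaluation: review follows recruitment of the cohort, so there is no pause within it.
- Decision table: counts only three event types, attributed to the statin. A death of another type, or one not attributed, does not count.
- Data Analysis: defines a safe regimen and attaches no hold.
- Algorithm for new cohorts: the readable consequence is no escalation. The consequence for the study is missing, the grade 4 limb could mean one participant or three, and deaths are not named.
- Early stopping rules: DSMB judgement, with no trigger or timing.
- Sections 5 and 9 on individual toxicities: stop drug for the participant, not enrolment.
- Sponsor or regulator termination (section 9) and immediate-hazard changes (section 19): available, but discretionary.

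None does so in readable form. Scenario 2 of the decision table goes the other way: five more people start a dose just judged unsafe. That dose is 40 mg, the recommended starting dose, so this is the lesser concern.

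**2. Do the DSMB calendars agree?** Cohort ends fall at 5, 5+10 = 15, 15+10 = 25 and 25+10 = 35, matching the plan's maximum of 35. Half of 35 is 17.5, which falls inside the 120 mg cohort and at no boundary. If the trial ends at 5, 15 or 25, the halfway point is 2.5, 7.5 or 12.5, and the final size is not known in advance. An annual review cannot recur within the estimated 6 months of recruitment.

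**3. Exposure before rifampin.** Assume that the dose proportionality stated in section 13 extends to these doses. Relative to 80 mg, exposure is then 120/80 = 1.5 times and 160/80 = 2.0 times.

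**4. How many starts could a hold delay?** Assumptions: even accrual, a cohort of 10, and an event in participant k on study day d, with reporting lag L days and interval i days between starts.

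Started = min(10, floor(((k-1)·i + d - 1 + L)/i) + 1). Not yet started = 10 - started, averaged over k = 1 to 10 with equal weight.

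| Accrual assumption | i (days) | L | d = 2 | d = 7 | d = 15 |
|---|---|---|---|---|---|
| 35 in 6 months | 182/35 = 5.2 | 0 | 4.5 | 3.6 | 2.8 |
| same | 5.2 | 3 | 4.5 | 3.6 | 2.1 |
| 35 in 12 months | 365/35 = 10.4 | 0 or 3 | 4.5 | 4.5 | 3.6 |
| 6 months less three 30-day pauses | (182-90)/35 = 2.63 | 0 | 4.5 | 2.8 | 1.0 |
| same | 2.63 | 3 | 3.6 | 2.1 | 0.6 |

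Example: i = 5.2, L = 0, d = 7, k = 1. Started = floor(6/5.2) + 1 = 2, so 8 have not started. Over k = 1 to 10 the counts are 8, 7, 6, 5, 4, 3, 2, 1, 0, 0, with mean 3.6.

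The averages span 0.6 to 4.5. Replacements and enrollees later found ineligible are not modelled.

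**The case against.** The strongest reply is that the algorithm for new cohorts was meant to act on the whole study. A consequence for the study was plainly intended, and the verb was lost in drafting or in reading the PDF. Grade 4 is headed potentially life-threatening in the protocol's severity tables, and the clause applies whatever the cause. On one reasonable reading, a single grade 4 event already stops the trial. This stands as a reason to call the rule unreadable rather than absent. It does not show that the rule exists, and on any reading the sentence names neither deaths nor a pause pending review.

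Second, a DSMB charter, the operations manual or the report schedule left open in section 10 may provide for notification. That also stands. None of these is in the documents, so the point concerns what the protocol itself secures.

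Third, oversight is not thin. The trial is open-label with daily adverse event assessment, the DSMB has a general monitoring role, SAEs reach DAIDS and regulators quickly, and individual stopping criteria are detailed. A reader might infer that the trial has no safety stopping provision or that the DSMB would be kept in the dark. The documents support neither inference.

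Fourth, the mismatches are mostly wording. The sentence on stopping rules can be squared with DSMB judgement, and the halfway and annual reviews can be read as additional to the cohort reviews. No dosing decision is shown to change.

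Fifth, the 6-month case without pauses is generous, because escalation has to wait for review. The rows with pauses fit the plan better, and most of their figures are lower.

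**Conclusion.** The point holds as a cheap improvement to the protocol, not as proof of a missing safety system. As written, DSMB review follows cohort recruitment, its approval gates only escalation, SAE distribution omits it, and no legible rule pauses new starts at the current dose after a death or life-threatening event. The main uncertainty is the damaged sentence in section 18, which may have been intended to do part of this.

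The averages of 0.6 to 4.5 participants not yet started rest on assumed even accrual, equal chance of the event across the ten participants, and the event days and lags shown. A reader might take them as people harmed or spared. They are neither: a hold delays those starts, and spares anyone only if the DSMB then stops the dose. The documents give no rate of life-threatening events, so no expected frequency can be given. The 1.5 and 2.0 exposure ratios depend on proportionality above 80 mg, concern two doses per person, and arise only in arms opened after lower doses have passed.

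**What to change.** 1. In the algorithm for new dosing cohorts (section 18), supply the missing consequence for the study, state whether one or three participants with a grade 4 event trigger it, name deaths, and say that the count applies as events accrue.
2. In section 5, add the DSMB to the recipients of the SAE reports already due within 3 days.
3. State that any death, or any life-threatening event not clearly due to another cause, puts new enrolment at that dose on hold until an ad hoc DSMB review replies. Include the five-participant extension at 40 mg. Leave further thresholds, and the management of participants already on drug, to the sponsor and the DSMB.
4. Replace the last sentence of Safety Evaluation with a cross-reference to section 18, and align the review calendar in section 10 with the cohort reviews.

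The cost is protocol wording, one more recipient for existing reports, and an occasional short pause with an unscheduled DSMB review. Some pauses will be for events caused by TB or the TB drugs. No new committee or participant procedure is needed.

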## **5. Adverse Events**

The Investigators are responsible for eliciting adverse events by observing study participants and recording all adverse events observed by him/her or reported by study participants during the trial.

### ***Definitions***

Adverse event (AE): Any untoward medical occurrence in a study participant administered a pharmaceutical product and which does not necessarily have a causal relationship with this treatment. An adverse event can therefore be any unfavorable and unintended sign (including an abnormal laboratory finding), symptom, or disease temporally associated with the use of a medicinal product, whether or not related to the medicinal product.

Serious adverse event (SAE): Any untoward medical occurrence that at any dose:

- results in death;
- is life threatening (any event in which the subject was at risk of death at the time of the event; it does not refer to an event, which hypothetically might have caused death if it were more severe);
- requires inpatient hospitalization or prolongation of existing hospitalization;
- results in persistent or significant disability/incapacity;
- is a congenital anomaly/birth defect; or
- is a medically important event.

Note:

Medical and scientific judgment should be exercised in deciding events are “medically important.” These events are those that may not be immediately life-threatening or result in death or hospitalization, but may jeopardize the study participant or may require medical or surgical intervention to prevent one of the outcomes listed above. Examples of such events are intensive treatment in an emergency room or at home for allergic bronchospasm, blood dyscrasias or convulsions that do not result in hospitalization, or the development of drug dependency or drug abuse.

Unexpected Adverse Event (UAE): An adverse reaction, the nature or severity of which is not consistent with the applicable product information (e.g., Investigator’s Brochure for an unapproved investigational product or package insert/summary of product characteristics for an approved product).

